The description of quantitative indicators (continuous or discrete) will be done using measures of central tendency (mean or median) and dispersion (standard deviation, interquartile ranges, and confidence intervals) according to their normality distribution. For the description of categorical variables (nominal and ordinal), absolute and relative frequency measures will be used. The R v.4.1.2 software will be used for the analyses ($p < 0.05$). The assumptions of normality and homoscedasticity will be verified using the Shapiro-Wilk and Levene tests, respectively. For variables that do not meet the assumption of normality, a two-step rank transformation will be applied. A two-way, repeated measures ANOVA will be used to determine intragroup and intergroup differences. Model effects are Group, Time, and their interaction over time (Group \times Time). Tukey's post hoc test will be used for variables with Group \times Time interaction. The statistical analyst will be blinded for the intervention groups, and in addition, an intention-to-treat analysis (multiple imputation method) will be considered for handling potential incomplete data. Clinical significance (ES) of interventions will be determined using Cohen's "d" (< 0.2 =negligible, $0.2-0.49$ =small, $0.5-0.79$ =moderate; ≥ 0.8 =large). Additionally, at the end of the intervention, patients will be asked to rate their overall change in clinical status (pain and functionality) using a 15-point scale. The global rating of change ranges from +7 ("a very great deal better") to 0 ("about the same") to -7 ("a very great deal worse"). The interpretation of changes is: 1-3 points=small, 4-5=moderate, and 6-7=large.

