The design is a two-arm parallel randomized clinical trial (RCT) and will be conducted according to the CONSORT statement. A control group (CG) will perform CPR, and an experimental group (EG) will perform AVG adjunct to CPR. Subjects will be invited to participate upon admission to the rehabilitation unit of a family health center. All study requirements will be explained, and all subjects will be required to sign an informed consent form.

Sample calculation.

The a priori calculated sample size using G*Power yielded 50 subjects. Statistical power $(1-\beta)=0.8$ and significance $(\alpha)=0.05$ were considered. In addition, a moderate effect size $(ES)=0.51$ was considered for the TUG test (functional mobility) to

detect a minimum clinically important difference (MCID) of 1.4 seconds. Ten subjects will be added for a potential dropout of 20%, finally estimating a sample of 60 subjects (CG=30; EG=30).

Participation criteria.

- Inclusion criteria: Age ≥ 60 and ≤ 84 years; Diagnosis of mild or moderate OA of the knee and/or hip; Independent walking capacity of at least 15 meters
- Exclusion criteria: Inability to interact with active video games; Undergoing treatment with opioids or other medications with a potential influence on the outcomes of interest; < 13 points in the abbreviated version of the Mini-Mental State Examination (MMSE-EFAM); OA associated with infectious, autoimmune, fractures or surgery; Participate or have participated in another physical-cognitive rehabilitation program during the last 3 months.

Randomization and allocation concealment.

A stratified randomization will be applied to balance the two study groups according to "age" (60-69, 70-79, 80-84 years) and "sex" (male, female). Allocation concealment will be ensured through sealed and consecutively numbered opaque envelopes.

Sample characterization.

Sociodemographic (age, sex, and education) and clinical characteristics (diagnosis of OA, comorbidity, history of falls, technical aids, and pharmacotherapy) will be collected by interview. In addition, height, body weight, and body mass index will be measured.

Study outcomes.

An experienced physical rehabilitation professional will perform the measurements in a blinded manner.

a) Primary outcome measure:

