- Functional mobility. Timed Up and Go (TUG). Number of seconds required to get up from seated position, walk 3 m, turn, and return to seated position on chair. Time Frame: Five-time points. Baseline (pre-intervention); at week 4 (after ten sessions from baseline); at week 7 (after 20 sessions from baseline); and week 10 (after 30 sessions from baseline). In addition, four weeks after the completion of the intervention.

b) Secondary outcome measures:

- Lower body strength: 30-s chair stand. Number of full stands in 30 s with arms folded across chest. Time Frame: Five-time points. Baseline (pre-intervention); at week 4 (after ten sessions from baseline); at week 7 (after 20 sessions from baseline); and week 10 (after 30 sessions from baseline). In addition, four weeks after the completion of the intervention.
- Upper body strength. 30-s arm curl. Number of bicep curls in 30 s holding hand weight (women 5 lb; men 8 lb). Time Frame: Five-time points. Baseline (pre-intervention); at week 4 (after ten sessions from baseline); at week 7 (after 20 sessions from baseline); and week 10 (after 30 sessions from baseline). In addition, four weeks after the completion of the intervention.
- Aerobic endurance. 2-min step test. Number of full steps completed in 2 min, raising each knee to point midway between patella and iliac crest (score is number of times right knee reaches target). Time Frame: Five-time points. Baseline (pre-intervention); at week 4 (after ten sessions from baseline); at week 7 (after 20 sessions from baseline); and week 10 (after 30 sessions from baseline). In addition, four weeks after the completion of the intervention.
- Lower body flexibility. Chair sit-and-reach. From sitting position at front of chair, with leg extended and hands reaching toward toes, number of inches (+or –) from extended fingers to tip of toe. Time Frame: Five-time points. Baseline (pre-intervention); at week 4 (after ten sessions from baseline); at week 7 (after 20 sessions from baseline); and week 10 (after 30 sessions from baseline). In addition, four weeks after the completion of the intervention.

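### A Shapiro-Wilk result decides whether the primary TUG effect is estimated in seconds, and the SAP prespecifies no between-group difference in seconds to set against the 1.4 s MCID

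*Combined protocol and SAP*

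**What the plan says.** Protocol section 5, under Study outcomes, defines TUG in time units: "Number of seconds required to get up from seated position, walk 3 m, turn, and return to seated position on chair". It is measured at five time points. Under Sample calculation, the trial is sized to "detect a minimum clinically important difference (MCID) of 1.4 seconds", with an effect size of 0.51, power 0.8 and alpha 0.05. Specific objective 3 in section 4 is to evaluate clinical significance.

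The SAP then sets this sequence:

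- Check: "The assumptions of normality and homoscedasticity will be verified using the Shapiro-Wilk and Levene tests, respectively".
- Consequence: "For variables that do not meet the assumption of normality, a two-step rank transformation will be applied".
- Model: "A two-way, repeated measures ANOVA will be used to determine intragroup and intergroup differences", with Group, Time and Group × Time as effects.
- Clinical significance: Cohen's d and a 15-point global rating of change.
- Descriptive summaries: mean or median, depending on normality.

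The SAP does not exempt TUG from the transformation, name the two steps, or give a back-transformation. It does not say whether the check uses raw values or residuals, pooled or separate arms, or one visit or all. It does not mention the 1.4 s MCID.

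**The concern.** The trial is built around a difference in seconds, but the scale of its primary analysis is left to a significance test on its own data. If TUG fails that test, the ANOVA is fitted to transformed ranks. Ranking followed by normal scoring is non-linear, so a difference in change on that scale is not a difference in change in seconds. Rescaling to the original mean and SD brings back the unit but not the quantity.

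The stake is the size of the effect and its clinical reading. A significant Group × Time effect could be reported with no model-based estimate in seconds, or with one that looks like seconds and is wrong by an unknown amount. Either result would be a poor answer to specific objective 3 and to the question of whether 1.4 s was reached.

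**Working it through.** **1. The plan's own figures.** MCID 1.4 s and effect size 0.51 come from Sample calculation. If 0.51 is Cohen's d, the implied SD is 1.4 / 0.51 = 2.75 s. The stated total of 50 was not confirmed: a two-sided two-sample t-test at d = 0.51 needs 62 per arm, and the repeated-measures settings that give 46 to 52 need inputs the protocol does not state. That is a separate question, and nothing below depends on it.

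**2. Assumptions.** The documents give no TUG mean, shape or between-visit correlation, and do not define the two steps. The following are assumed:

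- lognormal TUG with mean 11 s and SD 2.75, 4 or 5.5 s;
- correlation 0.7 between baseline and week 10;
- 30 patients per arm;
- a true benefit of 1.4 s for every patient in the experimental group.

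Step one of the transformation is the fractional rank p over both visits pooled. Step two is y* = m + s × Φ⁻¹(p), where m and s are the pooled mean and SD.

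**3. How often the switch occurs, and what it does.** Shapiro-Wilk is run at the 0.05 level on the 60 pooled values at one visit.

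| SD (s) | Shapiro-Wilk rejects | True 1.4 s reads as | Ratio |
|---|---|---|---|
| 2.75 | 50% | 1.52 s | 1.52/1.4 = 1.09 |
| 4 | 79% | 1.64 s | 1.64/1.4 = 1.17 |
| 5.5 | 94% | 1.81 s | 1.81/1.4 = 1.29 |

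If TUG is normal, rejection is about 5% and the rescaled value is about 1.40 s.

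**4. If the scores are not rescaled.** In single-visit runs (30 per arm, SD 2.75 s, control means 10 and 12 s, normal and lognormal shapes), a uniform 1.4 s benefit becomes 0.49 to 0.67 normal-score units or 8.5 to 11.7 mean-rank units. Neither can be read directly against 1.4 s.

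**5. Direction of the error.** In the same lognormal runs, with the benefit confined to the slowest fifth of patients and a raw mean difference of about 1.4 s, the rescaled value is 1.33 to 1.36 s. The transformation can therefore understate as well as overstate, depending on who benefits.

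**6. What an estimate in seconds would look like.** For one visit, unadjusted, the 95% CI half-width is t × SD × √(2/n):

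- 30 per arm: 2.00 × 2.75 × √(2/30) = 1.42 s;
- 25 per arm: 2.01 × 2.75 × √(2/25) = 1.56 s.

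Staying in seconds does not change the planned sample size.

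**The case against.** The switch is written down in advance, the analyst is blinded to group, and randomisation keeps the test of no effect valid on either scale. All of that stands, and none of it supplies an estimate in seconds.

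The probability of a switch is undetermined. With the same lognormal at SD 2.75 s, rejection is 49% on the 60 pooled values in a separate run, 27% within one arm of 30 and 15% on change scores. This also stands: the documents support saying that the switch may occur, not that it will.

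The missing contrast in seconds is a gap even if TUG is normal and never transformed. That is correct, and it is why the fix does more than remove the pre-test.

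Descriptive summaries keep TUG in seconds. They do, but they are not the model-based contrast, and they may be medians in exactly the case where normality fails. Cohen's d does not fill the gap, because its scale is not stated.

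A reader might go further and infer any of the following, which the documents do not support:

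- **Transformed results can never be compared with 1.4 s.** With rescaling and mild skew the error is modest, about 9% in the first row of the table.
- **Testing all five visits makes the switch almost certain.** The SAP does not say that each visit is tested, or that one failure transforms them all.
- **Ranking removes the Time effect.** That would need standard normal scores computed separately at each visit. The SAP does not describe this, and it plans Time as a model effect.

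**Conclusion.** The point holds as a defect in the primary estimate and its interpretation, not in the validity of the test. It follows from the text alone that a preliminary test selects the scale of the primary analysis, that TUG is not exempt, and that no difference in seconds with a CI is prespecified.

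The size of the consequence is conditional on the assumed lognormal shape, mean, correlation, uniform benefit and two-step recipe. Over SD 2.75 to 5.5 s, the chance of a switch at one visit runs from about 50% to 94%, and the overstatement of a true 1.4 s from about 0.1 s to 0.4 s. With normal TUG both are negligible. Of these SDs, only 2.75 s ties to the plan's own figures, and only if 0.51 is Cohen's d. The larger SDs show sensitivity and are not predictions.

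**What to change.** Amend the SAP for TUG as follows:

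1. State that the primary Group × Time contrast is estimated in seconds whatever any normality test shows, and name the visit it refers to.
2. Report the mean between-group difference with a 95% CI and interpret it against 1.4 s.
3. Judge normality on model residuals. If they are skewed, obtain the CI by bootstrap or from robust standard errors.
4. Keep the two-step rank transformation as a sensitivity analysis, and define both steps.
5. State the scale on which Cohen's d is computed.

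The cost is SAP wording and one sensitivity analysis, with no change to the planned number of patients. The downside is some loss of power if TUG turns out to be very heavy-tailed.

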Conventional physical rehabilitation (CPR) consists of traditional physical exercises that improve functional capacity (22,23). Over the past few years, it has been suggested that incorporating AVGs into CPR can optimize clinical and psychosocial outcomes in the elderly (24-26). AVGs have been reported to promote improvements in functional mobility, coordination, muscle strength, and cognitive function in older people (27-29). In addition, AVGs improve walking ability (30) and postural balance (31), as well as social well-being (perception of loneliness, social connectedness, and positive attitudes) (24). However, this research has focused on healthy elderly (30-33) and patients with neurocognitive pathologies (29,34-37). On the other hand, little information is available on older people with musculoskeletal conditions such as OA (38-40). In this regard, a systematic review conducted in patients with knee and/or hip OA indicates that the evidence is insufficient and inconclusive regarding the effectiveness of AVGs (38). Moreover, one study concludes that AVGs are a feasible and acceptable intervention for patients with knee OA (39). Interestingly, both studies raise the benefits and potential of AVGs in this population, urging further clinical trials (38,39).

3. RESEARCH QUESTION AND HYPOTHESIS.

- **Research question:** In older adults with knee and/or hip OA. Is AVG-guided physical exercise adjunct to CPR more effective than CPR alone in improving clinical and psychosocial outcomes?
- **Working hypothesis:** In older adults with knee and/or hip OA, AVG-guided physical exercise adjunct to CPR is more effective than CPR alone in improving clinical and psychosocial outcomes.

4. OBJECTIVES.

General objective: To determine the effects of an AVG-guided physical exercise program adjunct to CPR on clinical and psychosocial outcomes in older adults with knee and/or hip OA attended at a community-based family health center.

Specific objectives:

1. To characterize the study sample from sociodemographic, anthropometric, clinical, and psychosocial perspectives.
2. To compare the results of the primary outcome (functional mobility) and secondary outcomes between the study groups (experimental and control) in the different instances of outcome measurement.
3. To evaluate the clinical significance of the interventions and the clinical relevance of the interventions as perceived by the participants.

5. METHODS.

Study design and setting.

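### The primary TUG analysis names no deciding term or visit, does not adjust for baseline TUG, and states no sphericity correction for its five-visit F test

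*Combined protocol and SAP*

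**What the plan says.** The protocol (section 5, Study outcomes) makes TUG, in seconds, the primary outcome. It is measured at baseline, weeks 4, 7 and 10, and four weeks after the intervention ends. The sample calculation rests on a 1.4 s difference and an effect size of 0.51, and ties neither to a visit. Specific objective 2 (section 4) compares outcomes "between the study groups (experimental and control) in the different instances of outcome measurement", which ranks no visit above another.

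The SAP is one paragraph. On the model it says: "A two-way, repeated measures ANOVA will be used to determine intragroup and intergroup differences" and "Model effects are Group, Time, and their interaction over time". Tukey's "post hoc test will be used for variables with Group" x Time interaction. On assumptions: "The assumptions of normality and homoscedasticity will be verified using the Shapiro-Wilk and Levene tests, respectively". Sphericity is not mentioned. On non-normal variables: "For variables that do not meet the assumption of normality, a two-step rank transformation will be applied". On missing data: "an intention-to-treat analysis (multiple imputation method) will be considered for handling potential incomplete data". Cohen's d is planned as the measure of clinical significance, without a stated visit or contrast. Baseline TUG is not a model term, and neither are the randomisation strata (age band and sex).

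**The concern.** Three things needed to interpret the primary result are absent.

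- **Deciding term and visit.** A significant interaction would show that the arm difference is not the same at all visits. It would not show at which visit, by how many seconds, or whether that counts as the primary result.
- **Baseline adjustment.** If baseline is one of the five Time levels, which is the natural reading, Group x Time uses it as a difference. The Group effect and any raw comparison at a visit do not adjust for it, so they are less precise than the collected data allow.
- **Sphericity.** The uncorrected F test over five visits is exact only under sphericity. Visits spread over about 14 weeks may well have correlations that fall with distance in time, and the test then rejects too often.

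At stake are a clear statement about 1.4 s, the width of its interval, and the nominal 5% level of the interaction test.

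**Working it through.** **Inputs.** From the documents: 1.4 s; effect size 0.51; alpha 0.05; 50 evaluable subjects (60 randomised); five visits; two arms. Assumed, because the documents do not give them: 25 per arm analysed; 0.51 read as Cohen's d, so SD = 1.4/0.51 = about 2.75 s; the correlations between visits; the shape of the effect over time.

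**The plan's own figure.** The plan states no error rate or precision, only 50 subjects. A two-sided two-sample t-test at d = 0.51 with 80% power needs 62 per arm, so 50 is not reproduced on this reading. That is a separate matter; here 25 per arm is only the number analysed.

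**Step 1: what the interaction tests.** Its degrees of freedom are (2-1) x (5-1) = 4. The null hypothesis is that the arm difference is equal at all five visits. The F statistic carries no estimate in seconds.

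**Step 2: what could give a between-arm difference.** Cohen's d could, for a contrast not yet named. Tukey's test could, but its power depends on a family that is not stated. For 1.4 s at one visit the noncentrality is 0.51 x sqrt(25/2) = 1.80.

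- All 10 group-visit cells: 10 x 9/2 = 45 pairs, critical |t| 3.19 to 3.32 (240 to 48 df), power about 8%.
- The two arms within a visit: Tukey reduces to the t-test, power 42%.

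**Step 3: precision at one visit.** Raw SE = 2.75 x sqrt(2/25) = 0.778 s. Raw half-width = 2.011 x 0.778 = 1.56 s (48 df). ANCOVA half-width = 2.012 x 0.778 x sqrt(1-r²) (47 df), where r is the baseline-to-visit correlation. Power is from the noncentral t.

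| r | sqrt(1-r²) | ANCOVA half-width | ANCOVA power | Change-score power | Raw power |
|---|---|---|---|---|---|
| 0.5 | 0.866 | 1.36 s | 53% | 42% | 42% |
| 0.7 | 0.714 | 1.12 s | 70% | 63% | 42% |
| 0.8 | 0.600 | 0.94 s | 84% | 80% | 42% |
| 0.9 | 0.436 | 0.68 s | 98% | 98% | 42% |

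With 30 per arm, raw power is 49% and ANCOVA power is 61/78/90/99%.

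**Step 4: error of Group x Time.** Simulated with no effect, 25 per arm, 100,000 runs per setting (Monte Carlo SE about 0.1 point). Epsilon is the mean sample value.

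| Assumed correlation | Uncorrected | Greenhouse-Geisser |
|---|---|---|
| Constant, 0.5 to 0.9 | 4.9-5.1% | 4.4-4.6% |
| Mild decay (epsilon 0.85 and 0.76) | 5.5% and 6.1% | 4.6% |
| AR(1), adjacent visits 0.7/0.8/0.9 (epsilon 0.66/0.61/0.57) | 7.1/7.5/8.0% | 4.8/4.8/4.9% |

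A fresh simulation of 60,000 runs per setting agreed within 0.3 points.

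**Step 5: cost of choosing one visit.** Power at constant correlation 0.7, uncorrected Group x Time against week-10 ANCOVA. Week 10 is illustrative only.

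| Arm difference at the five visits (s) | Group x Time | Week-10 ANCOVA |
|---|---|---|
| 0/0.47/0.93/1.4/1.4 | 61% | 69% |
| 0/1.4/1.4/1.4/1.4 | 63% | 69% |
| 0/0.35/0.7/1.05/1.4 | 51% | 45% |
| 0/1.4/1.4/0.7/0.7 (early peak) | about 57% | 23% |

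Neither test is better in every profile.

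**The case against.** **The error rate.** A reader might infer that the primary test has 5-8% error as it stands. The documents do not support that. They give no correlations between visits, and they are silent on a correction rather than ruling one out. The figure also applies only if a bare interaction counts as success. Under the written sequence, Tukey's test follows the interaction. A null simulation (25 per arm, 20,000 runs) required an uncorrected interaction plus at least one significant post-baseline arm difference. With an unadjusted t-test at each visit, this happened in 0.9-2.5% of trials under constant correlation and 1.8-3.0% under AR(1). With the 45-pair Tukey critical value it was 0.04-0.2%. These rates assume a separate between-subject standard error at each visit; another error term could give higher ones. So the inflation concerns the interaction test, not necessarily a claim about a visit.

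**Estimating the difference.** A reader might infer that the plan cannot give a between-arm difference. It can, through Tukey's test or Cohen's d; what is missing is the named contrast. It is also tempting to say that the rank transformation puts 1.4 s out of reach. The SAP does not describe its second step, which might map ranks back to a seconds-like scale.

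**The omnibus test.** An interaction driven by weeks 4 and 7 alone would be a true difference and would fit objective 2, so it is not a false positive. Step 5 shows that the omnibus test can be the more powerful choice. Preferring one visit is therefore the sponsor's decision, not a correction of an error.

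All of this stands. It does not supply a deciding term or visit, a sphericity rule or a baseline adjustment.

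**Conclusion.** The point holds in this limited form. The omissions can be read directly from the SAP and depend on no assumption.

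- **Interpretation.** The primary comparison has no deciding term or visit, and its omnibus test does not by itself estimate 1.4 s.
- **Precision.** At r = 0.7, ANCOVA shortens the interval from 1.56 to 1.12 s either side, about 28% (1 - 1.12/1.56). The seconds depend on 25 per arm and on 0.51 being d. If 0.51 is Cohen's f (d about 1.02), the SD and all half-widths halve and raw power is 94%, so little power is left to gain under constant correlation. The proportional narrowing is the same.
- **Error.** Uncorrected Group x Time error runs from nominal to about 8% over the covariances tried. Greenhouse-Geisser holds it at or just below 5% throughout.

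This should be fixed, but it is moderate: it affects clarity and efficiency and does not invalidate the trial. Power gives no ground for saying that the omnibus test must be abandoned.

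**What to change.** 1. Apply a Greenhouse-Geisser correction to the within-subject tests (Time and Group x Time) wherever the repeated-measures ANOVA is used.
2. Estimate the EG minus CG difference in TUG, in seconds with a 95% CI, at one visit that the sponsor names before unblinding. Use ANCOVA with baseline TUG as covariate and the randomisation strata (age band, sex) as factors. Fit it in each imputed data set, pool the results, and report the estimate against 1.4 s.
3. State whether this contrast or the corrected Group x Time test is primary, and label the other secondary.

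The cost is a few sentences in the SAP and standard R code, with no new data or visits. The correction is slightly conservative when sphericity holds (4.4-4.6%). If the single-visit contrast is made primary, it loses power when the effect peaks at another visit: in the early-peak profile about 23% against 57% at constant correlation 0.7. ANCOVA does not by itself secure 80% power: with 0.51 as d and 25 per arm, r must be about 0.8.

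### The SAP's only visit-level between-arm test is Tukey's, with no comparison family or error term stated; applied to all ten Group × Time cells, it would need an observed TUG difference of about 2.3 s

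*Combined protocol and SAP*

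**What the plan says.** Section 4 (Objectives), specific objective 2, calls for results to be compared "between the study groups (experimental and control) in the different instances of outcome measurement". Section 5 (Study outcomes) schedules TUG at five time points: baseline, weeks 4, 7 and 10, and four weeks after the intervention ends. Nine secondary outcomes share that schedule.

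The SAP fits a two-way repeated-measures ANOVA with Group, Time and their interaction, and gives it the task of showing both intragroup and intergroup differences. For follow-up, Tukey's "post hoc test will be used for variables with Group" × Time interaction. No other visit-level test is named. The SAP does not say which pairs Tukey covers, which error term or degrees of freedom it uses, or which visit is primary. Cohen's d is planned as an effect-size measure, without a stated contrast or visit.

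Section 5 (Sample calculation) says that "a moderate effect size $(ES)=0.51$ was considered for the TUG test", to "detect a minimum clinically important difference (MCID) of 1.4 seconds". It states no SD.

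**The concern.** Objective 2 needs one kind of comparison: arm against arm at the same visit. Tukey's procedure controls error over every pair in whatever family it is given, and here the family is left open. One choice makes the relevant contrasts pay for many others. Another leaves them uncorrected across visits. A third uses an error term that is wrong for a between-arm difference. The same TUG data could therefore pass or fail depending on a decision made after the data are seen, and the 1.4 s target lies inside the range of possible thresholds. The same gap affects the nine five-visit secondary outcomes.

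**Working it through.** **Inputs.** From section 5 (Sample calculation): target difference 1.4 s, effect size 0.51, alpha 0.05 (taken as two-sided), power 0.80, 30 per arm planned, and 25 per arm before the dropout allowance. Derived, not stated: SD = 1.4/0.51 = 2.745 s.

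**The plan's own figure.** "The a priori calculated sample size using G*Power yielded 50 subjects". A two-sided two-sample comparison with d = 0.51 needs 2 × (1.96 + 0.8416)²/0.51² ≈ 61 per arm, or 62 with the t distribution (124 in total). Fifty subjects give 42% power and 60 give 49%. The figure is not reproduced for a two-arm comparison. This is a separate issue, but it limits what any visit-level test can achieve.

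**Pair count.** 2 arms × 5 visits = 10 cells, and 10 × 9/2 = 45 pairs:
- 4 post-baseline, same-visit, between-arm pairs (objective 2)
- 20 within-arm pairs (2 × 10), which serve the SAP's intragroup aim
- 20 cross-arm pairs at different visits and 1 baseline between-arm pair: 21 that serve no stated aim

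**Thresholds.** SE of a same-visit difference = 2.745 × √(2/n), which is 0.709 s at 30 per arm and 0.776 s at 25. The threshold is the critical value × SE. For all-cells Tukey the critical value is q(0.95; 10, df)/√2. At 30 per arm it is 4.65/√2 = 3.29 with 58 df and 4.52/√2 = 3.19 with 232 df. Power is from the noncentral t for a true 1.4 s.

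| Procedure | 30 per arm | 25 per arm |
|---|---|---|
| Tukey, all 10 cells, between-subject SE | 2.26–2.33 s; 11–12% | 2.49–2.58 s; 8–9% |
| Bonferroni over the 4 contrasts | 1.83 s; 28% | 2.02 s; 23% |
| One unadjusted contrast | 1.42 s; 49% | 1.56 s; 42% |

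**Tukey on two arms within a visit.** With two means, Tukey's critical value equals the t value (2.002 at 58 df), so the threshold is the unadjusted 1.42 s. With no true effect, correlation 0.7 and no interaction gate, at least one of the four visits is falsely significant in about 12% of simulated trials.

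**All-cells Tukey with the within-subject error term.** The threshold becomes 3.195 × 0.709 × √(1 − ρ): 1.60, 1.24 or 1.01 s for an assumed correlation ρ of 0.5, 0.7 or 0.8. At 0.7 this is 1.24/0.709 = 1.75 true standard errors, about 8% two-sided error per contrast despite the nominal correction.

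**Interaction followed by all-cells Tukey.** Simulation with 30 per arm, SD 2.745 s, compound symmetry and assumed benefits of 0.5, 0.9, 1.4 and 1.4 s at the four post-baseline visits. A significant interaction with no post-baseline between-arm Tukey pair occurs in about 31%, 54% and 80% of trials at correlations 0.5, 0.7 and 0.85. A significant interaction together with at least one such pair occurs in only about 13–15% at each correlation. A time trend common to both arms changes none of these figures, because it cancels from the interaction and from the same-visit differences.

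**The case against.** Several points against the concern are sound.

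- A reader might infer that the plan prescribes all-pairs Tukey and that a difference must exceed 2.3 s. The SAP does not say so: all-cells is one reading, and the figure also depends on a back-calculated SD, full retention and a between-subject error term.
- A reader might count 41 of the 45 pairs as irrelevant. The SAP names intragroup differences as an aim, so 20 of those have a purpose and 21 do not. Even so, Bonferroni over the other 25 pairs would still need 2.29 s at 30 per arm.
- A reader might conclude that the trial's claim would rest on uncontrolled within-arm change. The Group × Time F test is itself a randomised comparison of change between arms, and the post hoc step does not affect it. What is lost is the result by visit.
- A reader might say that a successful trial would usually show an interaction but no between-arm pair. At correlation 0.5 that happens in only about 31% of trials. How often within-arm change would be flagged depends on a time trend that the documents do not give, so no rate is offered.
- The within-visit reading is not wholly unprotected. The gate is itself a 5% test, so if the arms differ at no visit it limits false findings. It does not do so across the remaining visits once one visit truly differs.
- Tukey does not conflict with the planned multiple imputation. Contrasts and standard errors can be pooled and a studentized-range critical value applied.
- Most of the shortfall from 80% power comes from the sample size: one unadjusted contrast has only 49%.

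These points narrow the finding. None supplies the missing family or error term.

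**Conclusion.** The concern holds in a limited form. The SAP leaves the only visit-level test for objective 2 undefined, and none of the three readings examined suits that objective. The all-cells reading with a between-subject SE raises the TUG threshold at 30 per arm from 1.42 s for one contrast, or 1.83 s for four, to about 2.3 s. It cuts power for a true 1.4 s from 49% or 28% to about 11–12%. The within-visit reading relies on the interaction gate alone for four visits. The within-subject error term can set the bar too low. The thresholds in seconds assume an SD of 2.745 s; the simulated rates also assume the stated benefits and compound symmetry. This is a weakness in the visit-level analysis that should be corrected. It does not invalidate the ANOVA.

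**What to change.** Replace the Tukey sentence in the SAP. For each outcome, estimate the between-arm difference with a 95% CI at every post-baseline visit, as planned contrasts from the model. Use the standard error appropriate to a between-arm difference, and do not make the contrasts conditional on a significant interaction. Adjust by Holm or a single-step multivariate-t method over those contrasts only, within each outcome:
- four for the five-visit outcomes
- two for MoCA and SF-12
- three for user satisfaction and therapeutic alliance

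If a primary TUG visit is named, test that contrast first without adjustment. Report within-arm changes separately with CIs, as description.

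The cost is SAP wording, plus the loss of formal within-arm tests, which the SAP currently lists as an aim. Against all-cells Tukey, the chance of detecting 1.4 s at a given visit roughly doubles, from 11–12% to 28% under Bonferroni over four. The change does not cure the sample-size shortfall, which needs its own answer.
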